- 6-months confirmed disability progression (6MCDP), is used in the IAP to keep consistent with the parent study IAP, although 3 months confirmed disability progression, 3MCDP, is defined in the CSP.
- As data provided from MRI vendor only contains absolute values for (all) T1-Gd+ lesions per assessment (no new T1-Gd+ lesions), in consequence (all) T1-Gd+ lesions per assessment will be used for definition of disease activity and for calculation of Combined Unique Active (CUA) lesions during MAGNIFY MS Extension Study. However, as MAGNIFY MS Extension Study only has yearly MRI assessments the number of "new" and "all" T1-Gd+ lesions can be considered identical (see also explanation in Section 9.8).

8 Analysis Sets and Subgroups

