9.10 Covariates and Stratification Factors

The following covariates are defined:

Unless otherwise specified, these factors will be obtained from the baseline information of the MAGNIFY MS Baseline.

Age

See MAGNIFY MS IAP version 3.0.

EDSS at Baseline

see MAGNIFY MS IAP version 3.0.

Pooled centers

Some centers will have few eligible participants only. Therefore, the centers will be pooled together by country except for

• sites that have more than 12 participants in the FAS (i.e., these sites will not be pooled with any other site).

Some countries will have few eligible participants only. Therefore, countries will be pooled as follows:

- Scandinavia = Finland and Sweden
- Mediterranean = Italy and Spain
- o France-UK = France and UK
- o Austria-Hungary-Czech = Austria, Hungary, and Czech Republic
- Australia-Canada = Australia and Canada

The following MRI specific covariate is defined:

Time between scans: in Years

Time between scans (in Years) is calculated as follows:

- Time between scans (in Years) = (MRI date of the Visit MRI of the previous Visit + 1) /365.25, i.e.:
 - If (Visit= Month 36) then Time between scans (in Years) = (MRI date at Month 36
 MRI date at Month 24 + 1)/365.25
 - If (Visit= Month 48) then Time between scans (in Years) = (MRI date at Month 48
 MRI date at Month 36 + 1)/ 365.25

If the corresponding MRI is available and the time between scans is missing (due to preceding MRI being missing) it will be replaced by expected time as follows:

- Month 36 Visit = 1 year
- Month 48 Visit = 1 year

For calculations for Month 1, 2, 3, 6, 12, 15, 18, 24 Visits, see MAGNIFY MS IAP version 3.0 Section 9.

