14.1.1 Primary Objective: Derivation and analysis of the primary endpoint

No Evidence of Disease activity (NEDA), also referred to as freedom from disease activity, is a new goal that is emerging in MS treatment. NEDA is a composite measure of disease activity, including relapses, cognition and disability progression, and MRI activity.

NEDA-3 during the Extension Study Period is defined as absence of the following three events during the Period:

- Qualifying Relapses
- 6-months Confirmed Disability Progression (6MCDP, see definition below)
- MRI Activity (i.e., presence of T1 Gd+ lesions and/or active T2 lesions)

NEDA-3 will be analyzed with the Kaplan-Meier (KM) time-to-event method to reduce the impact of unknown/missing information.

The start date will be the end date of M24 Visit + 1.

The event date will be defined as the minimum of

- the onset date of the first qualifying relapses during the Extension Study Period
- the start date of the first 6MCDP during the Extension Study Period (see definition below)
- the scan date of the first MRI during the Extension Study Period where at least one T1 Gd+ lesion or at least one active T2 lesion (see Section 9.8 for definition) is identified.

Imputation of partial onset dates of relapses is described in Section 9.7. Since full dates of MRI scan and EDSS assessment are mandatory, partial dates of 6MCDP, or MRI Activity are not expected.

If the participant did not experience any of the three events described above during the Extension Study Period, the minimum of the scan date of the last available MRI, the assessment date of the last available EDSS, and the Extension Study completion/discontinuation date will be used as the censoring date.

The time to disease activity (in months) will be calculated as [event date or censoring date as applicable – start date + 1]/30.4375. The number of participants at risk, failed, and survival rate (i.e., the proportion of participants with NEDA-3) along with the 95% CI will be estimated as per the KM method and reported at 6-months intervals. The KM survival curve will be plotted as well.

A descriptive summary of number and proportion of participants with event (overall and by type of event, i.e., qualifying relapse, 6MCDP, or MRI activity as the earliest event) and censored will be also presented.

6MCDP

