14.2 Secondary Endpoints

14.2.1 No Evidence of Disease Activity

As a secondary analysis, NEDA-3 during the following Periods (see definition in Section 9.6) will be analyzed similarly as in the primary analysis using the KM method:

Year 3 Visit Period

- Start date: end date of M24 Visit (see definition in Section 14.1.1) + 1
- Event date: same as in Section 14.1.1 accounting for events started during Year 3 Visit Period only
- Censoring date: the minimum of the scan date of the last available MRI during Year 3 Visit Period, the assessment date of the last available EDSS during Year 3 Visit Period, and the end date of Year 3 Visit Period (see definition in Section 9.6)

Year 4 Visit Period

- Start date: end date of M36 Visit + 1
- Event date: same as in Section 14.1.1 accounting for events started during Year 4 Visit Period only

• Censoring date: the minimum of the scan date of the last available MRI during Year 4 Visit Period, the assessment date of the last available EDSS during Year 4 Visit Period, and the Extension Study completion/discontinuation date

After start of study medication until end of Year 3 Visit Period

- Start date: date of Day 1 as defined in Section 9.5
- Event date: The event date will be defined as the minimum of
 - o the onset date of the first qualifying relapses during the Parent and Extension Study Period
 - o the start date of the first 6MCDP during the Parent and Extension Study Period
 - o the scan date of the first MRI during the Parent and Extension Study Period where at least one T1 Gd+ lesion or at least one active T2 lesion (see Section 9.8 for definition) is identified,

accounting for events started during "After start of study medication until end of Year 3 Visit Period" only.

• Censoring date: the minimum of the scan date of the last available MRI during "After start of study medication until end of Year 3 Visit Period", the assessment date of the last available EDSS during "After start of study medication until end of Year 3 Visit Period", and the end date of "After start of study medication until end of Year 3 Visit Period" (see definition in Section 9.6)

After start of study medication until end of Year 4 Visit Period (i.e. Parent and Extension Study Period)

- Start date: date of Day 1 as defined in Section 9.5
- Event date: same as for "After start of study medication until end of Year 3 Visit Period" accounting for events started during "After start of study medication until end of Year 4 Visit Period"

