14.2.2 Time to First Disease Activity

Time to first disease activity is defined as the time to first occurrence of either qualifying relapse, or 6MCDP, or new or enlarging T2-hyperintense lesions (active T2 lesions), or new T1 Gd+ lesions. This will be evaluated for the following Periods with corresponding start dates defined below:

- Extension Study Period
 - Start date for time to first disease activity: end date of M24 Visit + 1 (as defined in Section 14.1.1)
- Parent and Extension Study Period

o Start date for time to first disease activity: date of Day 1 (as defined in Section 9.5)

Since events described above are the same events as in NEDA-3 definition, the event date will be defined the same as in Sections 14.1.1 or 14.2.1, accounting for only events started during the above Periods, respectively. If the participant did not experience any disease event during a Period, the minimum of the scan date of the last available MRI during this Period, the assessment date of the last available EDSS during this Period, and the Extension Study completion/discontinuation date will be used as the censoring date.

Time to first disease activity (in months) will be calculated as [event date or censoring date as applicable – start date of the Period + 1]/30.4375 and the 5%, 10%, 15%, 25% percentile and median time to first disease activity will be estimated using the KM method along with the 95% CI.

Analysis (Analysis Set)	Derivation	Statistical Analysis Methods	Missing data handling
Secondary er	ndpoint: Time from M24 Visit to	o first disease activity	
Secondary (FAS)	Time to event: [event date or censoring date as applicable – start date + 1]/30.4375 for disease activities started during Extension Study Period	KM time-to-event: 5%, 10%, 15%, 25% percentiles and Median time to disease activity will be estimated as per the KM method and reported along with the corresponding 95% CI.	Same as Section 14.1.1
Secondary (FAS by subgroup "Previous treatment with DMDs")	Same as above	Same as above with KM estimates reported by subgroup.	Same as Section 14.1.1
Secondary er	ndpoint: Time from initial dose	of cladribine tablets to first diseas	e activity
Secondary (FAS)	Time to event: [event date or censoring date as applicable – start date + 1]/30.4375 for	Same as above.	Same as above.
Secondary (FAS by subgroup "Previous treatment with DMDs")	disease activities started during Parent and Extension Study Period		

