14.2.3 Time to MRI Activities, 6MCDP, Qualifying Relapse and Treatment Start with Other DMDs

Time (in months) from the initial dose of cladribine tablets (i.e. start date = date of Day 1 as defined in Section 9.5) to the following events will be calculated as [event date or censoring date as applicable – start date + 1]/30.4375, and analyzed similarly as in Section 14.2.2 using the KM method.

- first new or enlarging T2 lesion
 - Event date: the scan date of the first MRI during the Parent and Extension Study Period where at least one active T2 lesion (see Section 9.8 for definition) is identified
 - Censoring date: participants with no active T2 lesion identified at any scans during the Parent and Extension Study Period will be censored at the scan date of the last available MRI during this Period
- first new T1 Gd+ lesion
 - Event date: the scan date of the first MRI during the Parent and Extension Study Period where at least one new T1 Gd+ lesion (see Section 9.8 for definition) is identified
 - Censoring date: participants with no new T1 Gd+ lesion identified at any scans during the Parent and Extension Study Period will be censored at the scan date of the last available MRI during this Period
- first 6MCDP, as measured by EDSS
 - Event date: the start date of the first 6MCDP during the Parent and Extension Study Period
 - 6MCDP during the Parent and Extension Study Period will be defined similarly as in Section 14.1.1 with just Extension Study Period replaced by Parent and Extension Study Period.
 - Censoring date: participants with no 6MCDP started during the Parent and Extension Study Period will be censored at the assessment date of the last available EDSS during this Period
- first qualifying relapse
 - Event date: the onset date of the first qualifying relapse during the Parent and Extension Study Period

 Censoring date: participants with no qualifying relapse reported during the Parent and Extension Study Period will be censored at the Extension Study completion/discontinuation date

Time (in months) from M24 Visit (i.e. start date = end date of M24 Visit + 1) to the following events will be calculated as (event date or censoring date as applicable – start date + 1/30.4375, and analyzed similarly as in Section 14.2.2 using the KM method.

- first new or enlarging T2 lesion
 - Event date: the scan date of the first MRI during the Extension Study Period where at least one active T2 lesion (see Section 9.8 for definition) is identified

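### The Day 1 version of time to first disease activity is defined with new T1 Gd+ lesions but dated by a rule that counts any T1 Gd+ lesion

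*SAP*

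**What the plan says.** Protocol Tables 1 and 3 list time to first disease activity over 4 years from the initial dose, with new T1 Gd+ lesions as one of the qualifying events. SAP 14.2.2 keeps that definition: "or new or enlarging T2-hyperintense lesions (active T2 lesions), or new T1 Gd+ lesions". It analyses the endpoint over two periods, one starting after the M24 Visit and one starting at Day 1.

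For the event date, SAP 14.2.2 states: "Since events described above are the same events as in NEDA-3 definition, the event date will be defined the same". It points to 14.1.1 for the Extension Study Period and to 14.2.1 for the Parent and Extension Study Period. The MRI part of the rule in 14.2.1 is "the scan date of the first MRI during the Parent and Extension Study Period where at least one T1 Gd+ lesion", with an active T2 lesion as the alternative trigger. The rule in 14.1.1 is "the scan date of the first MRI during the Extension Study Period where at least one T1 Gd+ lesion". Neither restricts T1 Gd+ lesions to new ones.

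SAP 7 explains why all T1 Gd+ lesions stand in for new ones in the extension. The MRI vendor supplies only absolute counts there, and the two counts can be treated as identical because the "MAGNIFY MS Extension Study only has yearly MRI assessments".

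For parent-study data the SAP keeps the two counts apart. SAP 9.8 refers to the parent analysis plan for a separate count of new T1 Gd+ lesions up to Month 24. SAP 14.2.3 dates its own component endpoint, over the same Day 1 period, by the first scan where "at least one new T1 Gd+ lesion (see Section 9.8 for definition) is identified".

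**The concern.** The endpoint and its event date describe different events. Over the extension the difference is disclosed and argued to be immaterial. Over the parent study it is neither disclosed nor argued, and the reason given for the extension does not carry over, because the parent scans are closely spaced and begin at Month 1. A lesion that was already enhancing before the first dose, and still enhances at an early scan, would be scored as disease activity after treatment although nothing new has appeared.

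The error can run in only one direction: too many events, too early. SAP 14.2.2 reports the 5%, 10%, 15% and 25% percentiles as well as the median, and the lower percentiles are the statistics most exposed to spurious events at the first scans.

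**Working it through.** The plan states no sample size, power or event figure for this endpoint, so there is no figure to reproduce. The check is a comparison of the text, followed by sensitivity arithmetic.

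**1. Definition against dating rule, Day 1 version**

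| Item | Source | T1 Gd+ lesions counted |
|---|---|---|
| Endpoint definition | Protocol Tables 1 and 3; SAP 14.2.2 | new |
| Event date of the composite | SAP 14.2.1, by reference from 14.2.2 | any |
| Event date of the T1 Gd+ component | SAP 14.2.3 text | new |
| NEDA-3 definition | Protocol 8.1.5; SAP 14.1.1 | any |

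The statement in 14.2.2 that its events equal the NEDA-3 events is therefore wrong for T1 Gd+ lesions.

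**2. Are early parent scans in scope?** The clock starts at Day 1. SAP 9.10 indicates the parent visits for which times between scans are calculated: "For calculations for Month 1, 2, 3, 6, 12, 15, 18, 24 Visits, see MAGNIFY MS IAP version 3.0". SAP 9.6 lists sequential MRI periods for the same months. The dating rule in 14.2.1 takes the first qualifying scan in the period and excludes none of these visits. Nothing in SAP 7 supports equating all with new over an interval of one month.

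**3. One participant traced through the rules.** Suppose a participant has a T1 Gd+ lesion at baseline that still enhances at Month 1, with no new T1 Gd+ lesion, no active T2 lesion, no relapse and no 6MCDP. Under 14.2.2 as written, the composite fails at the Month 1 scan. Under 14.2.3, none of the four component endpoints has an event. A composite defined as the earliest of its components should not be able to do this.

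**4. How many such cases move a reported percentile?** Protocol 5.1 requires parent MRI data from Month 18 or Month 24 and EDSS data from Month 24. Under the censoring rule in 14.2.2, eligible participants should therefore not be censored near Month 1, and the Kaplan-Meier estimate there is a simple proportion. The number of events that brings the curve down to 1 − p is p × N. With the 200 to 220 evaluable participants planned in protocol 1.1:

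- 5%: 0.05 × 200 = 10; 0.05 × 220 = 11
- 10%: 20 to 22
- 15%: 30 to 33
- 25%: 50 to 55

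These counts assume no true early event. Any true event by Month 1 lowers the number of persistent-only cases needed.

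**5. Illustration on assumed inputs.** The documents give neither the share with T1 Gd+ lesions at baseline (g), nor the share of those still enhancing at Month 1 without new activity (q), nor the true event share by Month 1 (e). Assume g = 20% to 60%, q = 10% to 50% and e = 5%, with persistence independent of true events.

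- False events at Month 1 = N × g × q × (1 − e). Low: 200 × 0.20 × 0.10 × 0.95 = 3.8. High: 220 × 0.60 × 0.50 × 0.95 = 62.7.
- Event-free share at Month 1 = (1 − e) × (1 − g × q). Low: 0.95 × 0.98 = 0.931. High: 0.95 × 0.70 = 0.665. Under a new-only rule it is 0.95.

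At the low end, 1 − 0.931 = 6.9% have an event at Month 1, so the 10% percentile is not reached there. At the high end, 33.5% do, and the 5%, 10%, 15% and 25% percentiles all fall at Month 1. The range is too wide to serve as an estimate.

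**The case against.** **The omission of new may be shorthand.** The tables in SAP 14.2.3 also drop the word for an endpoint whose text requires new lesions, and 14.2.2 admits only events that started in the period. This has some force as a guess at intent, but it does not repair the rule. An MRI event is dated by its scan, and a raw T1 Gd+ count does not separate an old lesion from a new one, so the restriction on when events started does not remove a persisting lesion.

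**The parent analysis plan may resolve it.** SAP 9 keeps parent-plan rules for parent data unless this SAP explicitly specifies others. SAP 14.2.1 does specify one. The parent plan is not among the documents, so how it handles early scans cannot be checked. The parent-period NEDA-3 rules visible here, for Courses 1 and 2, use only Months 6, 12, 18 and 24. The Day 1 rule carries no such limit. This uncertainty stands.

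**The consequence is limited.** The study is single-arm and exploratory, with no formal hypothesis test. SAP 14.2.3 reports the components over the same period, so a careful reader could notice a discrepancy. That is correct and bears on priority. It does not make the rule right.

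**A stronger reading.** A reader might infer that the Day 1 NEDA-3 analyses in 14.2.1 are faulty for the same reason. The documents do not support this. Protocol 8.1.5 and SAP 14.1.1 define NEDA-3 with T1 Gd+ lesions of any kind, so 14.2.1 follows its own definition. Rewriting only the Day 1 periods would also set them against the Course 1 and Course 2 rules in the same section.

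**Conclusion.** The concern holds for one analysis: time to first disease activity over the Parent and Extension Study Period in SAP 14.2.2. Its event date does not match its definition, and the all-equals-new argument in SAP 7 does not reach the parent scans. Followed literally, the SAP can date the composite before every one of its components.

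The direction of the bias is clear but its size is not. The one result tied to a figure in the documents is that, at 200 to 220 evaluable participants, 10 to 11 persistent-only cases at the Month 1 scan are enough to place the 5% percentile there. Any percentage of participants affected would rest on baseline prevalence and persistence that the documents do not give. The conclusion takes the SAP text as written, without sight of the parent analysis plan.

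The primary endpoint starts after the M24 Visit and is not materially affected. The same applies to the extension-period version of 14.2.2, where the substitution is disclosed and argued from yearly scanning.

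**What to change.** In SAP 14.2.2:

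- Correct the sentence that calls these the same events as NEDA-3.
- For scans assigned to visits up to M24, date the MRI event from the first scan with a new T1 Gd+ lesion by the SAP 9.8 count (as 14.2.3 already does) or an active T2 lesion.
- For the M36 and M48 scans, keep all T1 Gd+ lesions and refer to the explanation in SAP 7.

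Leave the Day 1 NEDA-3 analyses in 14.2.1 as they are. A new-only sensitivity analysis there is optional.

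The cost is a short text edit and the matching change to the event derivation. No new data are needed, because 14.2.3 already requires the new-lesion count for the parent period. When making the edit, check it against the parent analysis plan, which holds the rule for that count.

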9.4.1 Efficacy Analyses

All efficacy analyses will be performed on the Full Analysis Set (FAS) population (Table 6). In addition, the primary and secondary analyses may be repeated for other analysis populations, as described in the IAP.

Table 6: Analysis of Efficacy Endpoints

Endpoint	Statistical Analysis Methods		
Primary	Proportion of participants with NEDA-3 during 2 years of the extension study. NEDA-3 will be analyzed with a Kaplan-Meier (KM) time-to-event method to reduce the impact of unknown/missing information (assuming missing at random [MAR]).		
	The 95% confidence intervals (CIs) for KM estimate at the end of the 2 years period will be provided.		
	Statistical methods to handle any deviations from MAR will be detailed in SAP.		
Secondary	For the secondary analyses, the methods will be similar as for the primary analysis.		
CCI			

CI: Confidence Interval; KM: Kaplan-Meier; MAR: Missing At Random; NEDA-3: Three Parameter No Evidence of Disease Activity; SAP: Statistical Analysis Plan.

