Primary (FAS)	Time to event: [event date or censoring date as applicable – start date + 1]/30.4375	KM time-to-event: The number of participants at risk, failed, and survival rate (i.e., the proportion of participants with NEDA-3) along with the 95% CI will be estimated as per the KM method and reported at 6-months intervals. The KM survival curve will be plotted as well.	Imputation for partial dates is described in Section 9.7. Participants experienced no event will be censored as defined above (minimum of the scan date of the last available MRI scan, the assessment date of the last available EDSS, and the study completion/discontinuation date).		

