14.1.2 Primary Objective: Sensitivity Analyses of the Primary Endpoints

The robustness of the results of the primary analysis will be evaluated by the following:

- The primary analysis will be repeated on the TCS
- The primary analysis will be repeated by subgroup "Previous treatment with DMDs" on the FAS.

Analysis (Analysis Set)	Derivation	Statistical Analysis Methods	Missing data handling
	oint: Proportion of participants se of cladribine tablets	with NEDA-3 during Year 3 Visit a	and Year 4 Visit Period after
Sensitivity (TCS)	Same as in the Primary Analysis (see Section 14.1.1)	Same as in the Primary Analysis (see Section 14.1.1)	Same as in the Primary Analysis (see Section 14.1.1)
Sensitivity (FAS by subgroup "Previous treatment with DMDs")	Same as in the Primary Analysis (see Section 14.1.1)	Same as in the Primary Analysis (see Section 14.1.1) with KM estimates reported by subgroup.	Same as in the Primary Analysis (see Section 14.1.1)
Sensitivity (FAS)	Crude percentages and time to event with descriptive summaries for qualifying relapse, 6MCDP, or MRI activity and NEDA	A descriptive summary of number and proportion of participants with event A descriptive summary of time to earliest event (overall and by type of event, i.e., qualifying relapse, 6MCDP, or MRI activity).	Missings will be presented in a separate category

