 - Censoring date: participants with no active T2 lesion identified at any scans during the Extension Study Period will be censored at the scan date of the last available MRI during this Period
- first new T1 Gd+ lesion
 - Event date: the scan date of the first MRI during the Extension Study Period where at least one new T1 Gd+ lesion (see Section 9.8 for definition) is identified
 - Censoring date: participants with no new T1 Gd+ lesion identified at any scans during the Extension Study Period will be censored at the scan date of the last available MRI during this Period
- first 6MCDP, as measured by EDSS
 - Event date: the start date of the first 6MCDP during the Extension Study Period (see definition in Section 14.1.1)
 - Censoring date: participants with no 6MCDP started during the Extension Study Period will be censored at the assessment date of the last available EDSS during this Period
- first qualifying relapse
 - Event date: the onset date of the first qualifying relapse during the Extension Study Period
 - Censoring date: participants with no qualifying relapse reported during the Extension Study Period will be censored at the Extension Study completion/discontinuation date
- treatment start with other DMDs

- Event date: the start date of the first other DMDs used during the Extension Study Period
- Censoring date: participants who did not use any other DMDs during the Extension Study Period will be censored at the Extension Study completion/discontinuation date

A recurrent event analysis will be performed on all qualifying relapses using the Mean Cumulative Function (MCF) method, where MCF(t) represents the mean cumulative number of relapses up to time t. The MCF estimate for recurrent events will be calculated and plotted for all qualifying relapses. The MCF Nelson estimates will be presented for every month along with their 95% CIs. The increase in MCF in each month, defined as MCF(t) - MCF(t-1) will also be displayed.

Time (in months) from the initial dose of cladribine tablets (i.e. start date = date of Day 1 as defined in Section 9.5) to each event and to censoring (as defined below) will be calculated as [event date or censoring date – start date + 1/30.4375, and analyzed using the MCF method.

- recurrent qualifying relapse
 - Event date: the onset date of each qualifying relapse during the Parent and Extension Study Period

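### For first relapse, first 6MCDP and start of other DMDs, SAP 14.2.3 plans Kaplan-Meier percentiles but no event-free proportion with CI, a departure from Protocol Table 6 that SAP Section 7 does not list

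*SAP*

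**What the plan says.** **Percentiles.** For time to first disease activity, SAP 14.2.2 specifies that "the 5%, 10%, 15%, 25% percentile and median time to first disease activity will be estimated using the KM method along with the 95% CI". Section 14.2.3 then has the times to each separate event "analyzed similarly as in Section 14.2.2 using the KM method", and its table refers back to 14.2.2 for the method. This covers first qualifying relapse and first 6MCDP (each from Day 1 and from the M24 visit) and start of other DMDs (from M24 only). The two MRI endpoints share the format but are not the subject of this point.

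**Event-free proportions.** The SAP names a KM proportion for the NEDA-3 composite. In 14.1.1 the "survival rate (i.e., the proportion of participants with NEDA-3) along with the 95% CI will be estimated as per the KM method", reported every six months with a plot. Section 14.2.1 does the same for the other NEDA-3 periods.

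**Protocol.** Table 6 says of the primary endpoint: "The 95% confidence intervals (CIs) for KM estimate at the end of the 2 years period will be provided". It adds: "For the secondary analyses, the methods will be similar as for the primary analysis". SAP Section 7, which lists changes from the protocol analyses, does not mention a different output for these endpoints.

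**Other planned outputs.**
- Relapse: a mean cumulative function (MCF) in 14.2.3, where "The MCF Nelson estimates will be presented for every month along with their 95% CIs".
- Relapse and 6MCDP: crude results in 14.1.2 and 14.2.1, described as "A descriptive summary of number and proportion of participants with event", with missing as a separate category.
- DMDs: a table by preferred term in SAP Section 12, pooling parent and extension periods, with no time element.

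**The concern.** A KM percentile is a time, and it exists only when the estimated cumulative incidence reaches that level during follow-up. An endpoint reported only through percentiles can therefore have empty cells, and how many depends on an event rate that nobody has stated. The long-term question is what share of participants remained free of relapse, free of confirmed progression, or off other DMDs through the extension. A KM proportion at a fixed time answers that at any event rate, and the protocol's wording leads a reader to expect it.

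DMD start is the most exposed. It is not a component of NEDA-3, so the crude summaries do not cover it, and it has no MCF. It is also an interim-analysis endpoint (SAP 6.1), at about 12 months of follow-up, when fewer percentiles will have been reached.

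Extension-period 6MCDP has a further difficulty. Both EDSS assessments must fall inside the period and be at least 166 days apart, while the scheduled visits are at 12 and 24 months after M24. Apart from EDSS obtained in the gap period or at unscheduled visits, an event can start only at about the M36 visit. Percentile times that are reached will then cluster near 12 months and mainly reflect the visit schedule.

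**Working it through.** **Inputs from the documents.** At most 256 enrolled for 200 to 220 evaluable (Protocol 1.1). Implied loss is 1 − 220/256 = 14.1% to 1 − 200/256 = 21.9%. Visit 2 is 720 days after M24 (SAP 9.5), or 720/30.4375 = 23.7 months. The documents give no event rate for relapse, 6MCDP or DMD start, so there is no planned figure to reproduce and two-year incidence *p* is an assumption, varied below.

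**Step 1, complete follow-up.** The *q* percentile is reached if the number of events is at least *nq*. For n = 220 that means 11, 22, 33, 55 and 110 events for the 5%, 10%, 15%, 25% and 50% points. Exact binomial probabilities of reaching each:

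| Assumed p | 5% | 10% | 15% | 25% | Median |
|---|---|---|---|---|---|
| 5% | 0.543 | 0.002 | 0 | 0 | 0 |
| 10% | 0.998 | 0.533 | 0.012 | 0 | 0 |
| 15% | 1 | 0.988 | 0.529 | 0 | 0 |
| 20% | 1 | 1 | 0.977 | 0.041 | 0 |
| 30% | 1 | 1 | 1 | 0.957 | 0 |
| 40% | 1 | 1 | 1 | 1 | 0.002 |

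At n = 200 and p = 40% the chance of reaching the median is 0.003.

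**Step 2, with censoring.** KM simulation: n = 220, exponential event times, 18% loss (the middle of the implied range), follow-up ending at 24 ± 1 months, log-log limits, 1000 runs.

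| Assumed p | Chance reached: 5 / 10 / 15 / 25 / 50% | Finite upper limit: 5 / 10 / 15 / 25 / 50% | Mean reached of 5 |
|---|---|---|---|
| 5% | 0.49 / 0.01 / 0 / 0 / 0 | 0.04 / 0 / 0 / 0 / 0 | 0.5 |
| 10% | 0.99 / 0.52 / 0.04 / 0 / 0 | 0.82 / 0.03 / 0 / 0 / 0 | 1.6 |
| 15% | 1 / 0.98 / 0.54 / 0 / 0 | 1 / 0.63 / 0.04 / 0 / 0 | 2.5 |
| 20% | 1 / 1 / 0.96 / 0.08 / 0 | 1 / 0.98 / 0.50 / 0 / 0 | 3.0 |
| 25% | 1 / 1 / 1 / 0.57 / 0 | 1 / 1 / 0.96 / 0.03 / 0 | 3.6 |
| 30% | 1 / 1 / 1 / 0.97 / 0 | 1 / 1 / 1 / 0.44 / 0 | 4.0 |

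Results at n = 256 are close. A 48-month version shows the same pattern at the same cumulative incidence, for example 1.55 of 5 reached at 10%.

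**Step 3, the alternative output.** The event-free proportion can be estimated at every rate in the table. Its approximate 95% half-width is 1.96 × √(p(1 − p)/n). At n = 220 with complete follow-up this is ±2.9 points at 5%, ±4.0 at 10%, ±4.7 at 15%, ±5.3 at 20% and ±6.1 at 30%.

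**Step 4, what the crude proportion loses.** With p = 10% and 18% loss, the two-year hazards are λ = −ln 0.90 = 0.105 and μ = −ln 0.82 = 0.198. The expected crude proportion is λ/(λ + μ) × (1 − 0.90 × 0.82) = 0.347 × 0.262 = 9.1%, about 0.9 points low. That is a modest error, and no CI is stated for the crude figure.

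**The case against.** A reader might infer that percentiles are all the SAP reports for these endpoints and that the tables will come back mostly not estimable. The documents do not support that.

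- **Other outputs exist.** Relapse has monthly MCF estimates with CIs. Relapse and 6MCDP have crude proportions, both for the extension and from first dose. By Step 4 the crude figure is not far off if drop-out is as assumed. This stands, and it confines the gap to the KM proportion with its CI. The MCF is a mean number of relapses, so it does not replace the proportion relapse-free.
- **Non-estimability depends on the rate.** The conclusion reverses between about 15% and 20% incidence, and no rate is given. SAP version 2.0 added a percentile summary to 14.2.2, so the plan does not rely on the median alone. A 10% time that is not reached is itself informative: the KM event-free estimate stayed above 90%. This stands.
- **Follow-up is not always two years.** Relapse and 6MCDP are also analysed from Day 1 over nominally four years, where cumulative incidence can only be higher. This stands, but DMD start has no such analysis.
- **The wording excludes nothing.** Analysing endpoints similarly to 14.2.2 does not forbid further rows, Protocol Table 6 already points to the KM estimate, and redacted SAP pages follow 14.2.3. This is fair, but an output that matters should be named, and 14.2.3's own table sends the programmer only to 14.2.2.
- **The study is exploratory, with no hypothesis test.** This limits the severity. It does not affect the case for a clearer table.

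**Conclusion.** The point holds as a minor reporting gap. The visible SAP text names no KM event-free proportion with 95% CI at a fixed time for first relapse, first 6MCDP or DMD start. This differs from what Protocol Table 6 implies, and Section 7 does not declare it. That part needs no assumption about event rates.

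The size does depend on such assumptions. The median is very unlikely to be reached in the 24-month analyses: never in simulation at 5% to 30% incidence, and with probability at most 0.003 at 40%. Below about 15% two-year incidence, half or more of the five percentiles are likely to be missing, and upper limits are rarer still. From about 20% most point estimates are reached.

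The gap is largest for DMD start, whose only other visible output is a table by preferred term. It is smaller for 6MCDP, which has crude proportions without censoring adjustment or a stated CI, and smallest for relapse.

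**What to change.** In SAP 14.2.3, alongside the percentiles:

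- From M24, for first qualifying relapse, first 6MCDP and start of other DMDs: report the KM event-free proportion with 95% CI at 12 and 24 months.
- From Day 1, for relapse and 6MCDP: report the same at 24, 36 and 48 months.
- Include the KM plot and the number at risk at each time. Visit 2 is nominally at 23.7 months on the SAP's conversion, so many participants may be censored just before 24 months, and the reader should see how many remain.

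This restores agreement with Protocol Table 6. If the sponsor prefers percentiles only, Section 7 should list that as a change.

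The cost is a few lines of SAP text and some extra table rows and plots from the same KM procedure and data. No additional data collection is needed.
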